### **11.3.9.2 Analysis of second supplementary estimand for continuous endpoints**

#### **Primary analysis**

All observed data will be included in the analysis, including data observed after the occurrence of intercurrent events.

Missing data will be imputed using MI (100 iterations) under a MAR assumption within each treatment group. All observed data will be used to inform the imputation model. Further details regarding the specification of the imputation models will be detailed in the SAP.

For each of the 100 complete datasets, the response will be analyzed using an ANCOVA model adjusted for treatment, baseline disease severity (baseline vIGA-AD score), region (Japan, Other countries), and prior use of biologics or systemic JAK inhibitors for AD (Yes/No). The model will also be adjusted for the baseline value of the dependent variable.

The pooled estimate of the difference in the LSmean change from baseline, along with the associated 95% CIs and nominal p-values will be presented. Inference will be based on applying Rubin's rules to the estimates and standard errors from the ANCOVA analysis of the imputed datasets.

### **11.3.9.3 Analysis of supplementary estimand for binary endpoints**

#### **Primary analysis**

All observed data will be included in the analysis, including data observed after the occurrence of intercurrent events.

Missing data will be imputed using MI (100 iterations) under a MAR assumption within each treatment group. All observed data will be used to inform the imputation model. Further details regarding the specification of the imputation models will be detailed in the SAP.

THIS DOCUMENT CONTAINS CONFIDENTIAL INFORMATION AND MUST NOT BE COPIED OR MADE AVAILABLE TO ANY THIRD PARTY WITHOUT THE PRIOR WRITTEN CONSENT OF THE LEO PHARMA GROUP

For each of the 100 complete datasets, the response will be analyzed using a logistic regression model including treatment, baseline disease severity (vIGA-AD score at baseline), region (Japan, Other countries), prior use of biologics or systemic JAK inhibitors for AD (Yes/No) and the baseline value of the endpoint as a covariate. For the analysis of the vIGA-AD responder endpoints, baseline disease severity will not be included as a factor in the logistic regression model.

The pooled estimate of the estimated risk differences and standard errors based on the standardized estimator presented in Bartlett (80), along with the associated 95% CIs and nominal p-values will be presented. Inference will be based on applying Rubin's rules to the estimates and standard errors from the analyses of the imputed datasets.

#### 11.3.9.4 Analysis of supplementary estimand for time to event endpoint

##### Primary analysis

Let  $T$  represent the time from baseline to the initiation of rescue treatment or permanent discontinuation of IMP, whichever occurs first. The *composite* estimand evaluates:

$$Pr(T < C_{admin})$$

where  $C_{admin}$  is the end of the treatment period (administrative censoring time), corresponding to Week 16.

The null hypothesis,  $H_{0,i}: \lambda_{\text{LEO 138559, regimen } i}(t) = \lambda_{\text{placebo}}(t), \forall t \in (0,16)$ , where  $\lambda(t)$  denotes the hazard rate associated with the time-to-event endpoint at time  $t$  (measured in weeks) and  $i \in (1,2,3,4)$  denotes the LEO 138559 dose regimen, will be tested against the alternative,  $H_{A,i}: \lambda_{\text{LEO 138559, dosage regimen } i}(t) \neq \lambda_{\text{placebo}}(t)$  based on the log-rank test, stratified by baseline disease severity (baseline vIGA-AD score), region (Japan, Other countries), and prior biologics or systemic JAK inhibitors for AD (Yes/No).

To quantify the magnitude of the potential treatment effect, the estimated cumulative incidence functions will be presented for the treatment groups, based on the Kaplan-Meier estimator, along with 95% CIs. Additionally, the difference in the estimated cumulative incidence functions at Week 16 between the LEO 138559 dose regimens and placebo will be presented along with 95% CIs.

#### 11.3.10 Analysis of baseline subgroup estimands

The baseline subgroup estimands will be analyzed according to the primary analysis for the primary estimand for binary endpoints, specified in Section 11.3.8.2.

THIS DOCUMENT CONTAINS CONFIDENTIAL INFORMATION AND MUST NOT BE COPIED OR MADE AVAILABLE TO ANY THIRD PARTY WITHOUT THE PRIOR WRITTEN CONSENT OF THE LEO PHARMA GROUP

### 11.3.11 PRO analysis

Endpoints related to PROs will be analyzed as described in Section [11.3.7](#).

### 11.3.12 PD

For the following endpoints, explorative analyses will be performed for the total population as well as by baseline disease severity:

- Change in expression of biomarkers in serum from baseline to Week 2, Week 4, and to Week 16, respectively.
- Change in skin *Staphylococcus aureus* abundance and microbiome profile from baseline to Week 16.
- Change in skin lipid and molecular profile from baseline to Week 4, and to Week 16, respectively.
- Change in biomarker expression from baseline to Week 16 in lesional skin biopsies.

A summary of the results will be included in the CTR if the results are available in time for this. The full set of biomarker results will be reported in an addendum to the CTR.

### 11.3.13 Safety analysis

The analysis of safety will be based on the safety analysis set.

#### 11.3.13.1 AEs

##### Coding of AEs

AEs will be coded during the course of the trial according to MedDRA. AEs defined by MedDRA PTs within primary SOC will be presented.

##### TEAEs

An event will be considered treatment-emergent if started after the first dose of IMP or if started before the first dose of IMP and worsened in severity after first dose of IMP. An event will not be considered treatment-emergent if starting 18 weeks after the last dose of IMP. The tabulations described in the following will only include the TEAEs. All AEs recorded during the course of the trial will be included in subject data listings.

AEs will be summarized in terms of the number of subjects with at least 1 event, the percentage of subjects with at least 1 event, the number of events, and the event rate per 100 patient years of observation time.

Related AEs are defined as AEs for which the investigator has not described the causal relationship to IMP as 'not related'. The number of related AEs and the number of subjects with each type of related AE will be tabulated.

THIS DOCUMENT CONTAINS CONFIDENTIAL INFORMATION AND MUST NOT BE COPIED OR MADE AVAILABLE TO ANY THIRD PARTY WITHOUT THE PRIOR WRITTEN CONSENT OF THE LEO PHARMA GROUP

An overall summary of the number of events and the number (percentage) of subjects with any TEAEs, deaths, SAEs, AESIs, permanent discontinuations from IMP and/ or withdrawals from the trial due to AEs, treatment-related AEs, and severe AEs will be presented.

Tabulations by SOC and PT will be presented for all AEs, SAEs, related AEs, AESIs, and AEs leading to withdrawal from trial and/or permanent discontinuation of IMP. In addition, all AEs will be presented by severity and causal relationship to IMP, respectively.

SAEs will be evaluated separately, and a narrative will be given.

AEs leading to withdrawal from trial or permanent discontinuation of IMP will be tabulated and listed. No narratives will be given.

Other events (medication error) will be listed. No narratives will be given.

#### **11.3.13.2 Vital signs**

The change in vital signs (resting BP, pulse, and body temperature) from baseline to each relevant visit will be summarized as mean, SD, median, minimum, and maximum values for each treatment group. Shift table for clinically significant abnormal vital signs will be presented.

#### **11.3.13.3 ECG**

Subjects with abnormal, clinically significant ECG will be listed. Furthermore, a shift table for ECG showing the change from baseline to end-of-treatment in clinical assessment (normal; abnormal, not clinically significant; abnormal, clinically significant) will be provided.

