THIS DOCUMENT CONTAINS CONFIDENTIAL INFORMATION AND MUST NOT BE COPIED OR MADE AVAILABLE TO ANY THIRD PARTY WITHOUT THE PRIOR WRITTEN CONSENT OF THE LEO PHARMA GROUP

[figure not shown]
The dose regimens selected for the trial are based on the PK data from the FiH phase 1 (LP0145-1315) trial, a phase 1 (LP0145-1486) trial, and a phase 2a trial (LP0145-1376) pooled in a population PK model. The efficacy data from these trials have also been used to guide the dose selection, and the preliminary PK/PD model suggests correlation between [REDACTED], exposure, and response. Due to the limited data from the phase 2a trial, a subgroup analysis based on [REDACTED] is associated with high uncertainty, but the data suggest that [REDACTED] subjects [REDACTED] would benefit from a higher dose than in the phase 2a trial (LP0145-1376, 450 mg Q2W). No safety concern is thought to be associated with higher exposure in [REDACTED] subjects, as only mild and moderate AEs have been observed in the completed clinical trials and there was no apparent correlation between exposure and AEs. The rationale for the dose selection is also described and summarized in a separate document that also includes details of the population PK model (78).

Based on the available efficacy and safety data from completed clinical trials and in order to identify a dose which can provide maximum efficacy in this patient population, a dose regimen of [REDACTED] mg loading dose at Week 0, 1, 2, 3 (to reach steady-state concentrations faster), followed by [REDACTED] mg Q2W dosing from Week 4 onwards (dose regimen 1) is included in the planned phase 2b trial. With this dose regimen, it is predicted that maximum serum concentration ( $C_{max}$ ) will be reached by Week 4 [REDACTED]  $\mu$ g/mL in a 75-kg subject) (Panel 13). The predicted average  $C_{max}$  is below the maximum observed serum concentrations in the phase 2a trial (LP0145-1376).

THIS DOCUMENT CONTAINS CONFIDENTIAL INFORMATION AND MUST NOT BE COPIED OR MADE AVAILABLE TO ANY THIRD PARTY WITHOUT THE PRIOR WRITTEN CONSENT OF THE LEO PHARMA GROUP

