### Safety assessments

Standard clinical methods of subject evaluations, such as AE monitoring (Section 10), vital signs, physical examination, ECG, laboratory testing including pregnancy testing, and ADA will be used to assess subject safety (Section 8.4). Given some large proteins may cause indirect adverse cardiac effects upon long-term exposure, data on ECG will be collected and evaluated (Section 8.4.4). Data on ADA will be collected in order to evaluate the potential immunogenicity of LEO 138559 (Section 8.4.6).

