## 11.3 Statistical analysis

### 11.3.1 General principles

Baseline measurements are defined as the latest available observation at or prior to the date of the first IMP administration, unless otherwise specified.

All significance tests will be two-sided using the 5% significance level. All CIs will be presented with 95% degree of confidence, unless otherwise specified. LSmeans will be estimated using the observed margins for the FAS.

THIS DOCUMENT CONTAINS CONFIDENTIAL INFORMATION AND MUST NOT BE COPIED OR MADE AVAILABLE TO ANY THIRD PARTY WITHOUT THE PRIOR WRITTEN CONSENT OF THE LEO PHARMA GROUP

An observed-cases approach will be used for tabulations of data by visit (that is, involving only those subjects who attended each specific visit).

Categorical data will be summarized using the number and percentage of subjects in each category and treatment group. Continuous data will be summarized using the mean, SD, median, 1st quartile and 3rd quartile, minimum, and maximum values.

All the analyses specified in the protocol will be reviewed in relation to the blinded data actually obtained, and the SAP will be finalized before breaking the randomization code.

Any changes from the statistical analyses planned in this clinical trial protocol will be described and justified in a protocol amendment, the SAP and/or in the CTR, dependent on the type of change.

Unless otherwise stated, efficacy analyses will be performed based on the FAS, safety analyses will be based on the safety analysis set, and PK analyses will be based on the PK analysis set.

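### ECG assessments are tabulated only as a shift from baseline to end of treatment, so three of the four scheduled post-baseline ECG visits feed no ECG table

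*Combined protocol and SAP*

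**What the plan says.** Section 11.3.13.3 names two ECG outputs. The first is a listing: "Subjects with abnormal, clinically significant ECG will be listed". The second is "a shift table for ECG showing the change from baseline to end-of-treatment in clinical assessment", on a three-level investigator rating: normal, abnormal without clinical significance, or abnormal with it. The section does not mention treatment groups. The by-arm layout follows from Section 11.3.1: "Categorical data will be summarized using the number and percentage of subjects in each category and treatment group".

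Both schedules of activities (Panel 2, and Panel 18 for EU countries) place ECGs at screening and at Weeks 0, 4, 8, 16 and 32. At early termination and unscheduled visits the ECG is marked as discretionary.

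The neighbouring safety sections work differently. For vital signs (11.3.13.2), the change "from baseline to each relevant visit will be summarized as mean, SD, median, minimum, and maximum values for each treatment group". Section 11.3.13.4 sets the same for laboratory parameters.

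Section 9.2 gives the reason for the ECGs: "Given some large proteins may cause indirect adverse cardiac effects upon long-term exposure, data on ECG will be collected and evaluated". On exposure, Section 9.1 says of dose regimen 1: "With this dose regimen, it is predicted that maximum serum concentration" "will be reached by Week 4".

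**The concern.** The trial collects ECGs at four post-baseline visits and tabulates one. An ECG that turns abnormal at Week 4 or 8 and is normal again at Week 16 sits in the no-change cell. A late abnormality at Week 32 is outside the table altogether. This is a dose-finding trial with four active regimens, and safety by regimen is its secondary objective. A reader will want to see whether ECG changes follow exposure over time and not only at one visit.

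The middle rating is the most exposed. It is one of the three categories in the shift table, so the plan treats it as worth counting at end of treatment. At the other three visits it is neither listed nor tabulated. No reason is given for handling ECGs more sparsely than vital signs and laboratory data.

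**Working it through.** The plan states no figure here, so the check is a count of visits against outputs.

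**Inputs.** Post-baseline ECG visits: Weeks 4, 8, 16 and 32 (Panels 2 and 18). Planned ECG outputs: one listing and one shift table (11.3.13.3). Adverse event route: Section 8.4.4 requires a new or worsened clinically significant ECG finding after screening to be reported as an adverse event, and Section 11.3.13.1 tabulates treatment-emergent events. Planned subjects: 250 (11.1).

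| Visit | In ECG shift table | Clinically significant finding visible elsewhere | Abnormal but not clinically significant finding visible |
|---|---|---|---|
| Week 4 | No | Listing; adverse event tables | No |
| Week 8 | No | Listing; adverse event tables | No |
| Week 16 (end of treatment) | Yes | Listing; adverse event tables | Yes, in shift table |
| Week 32 | No | Listing; adverse event tables, subject to the cut-off below | No |

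**Counts.** Visits outside the table: 4 − 1 = 3, and 3/4 = 75%. Within the treatment period the figure is 2 of 3 (Weeks 4 and 8 out of 4, 8 and 16). With full attendance, 250 × 4 = 1,000 ECGs are planned after baseline, of which 250 × 3 = 750 feed no ECG table.

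**Week 32 cut-off.** Section 11.3.13.1 stops counting events as treatment-emergent when they start 18 weeks after the last dose. The last dose is on Day 99 and the final visit on Day 225: 225 − 99 = 126 days = 18 weeks. An event dated to the Week 32 ECG may therefore fall outside the treatment-emergent tables.

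**Week 4 and exposure.** Section 8.1 puts dosing after all other assessments at a visit, so the Week 4 ECG precedes that day's dose. It is the scheduled ECG nearest the predicted maximum for regimen 1, but not necessarily at it.

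**Which ECG is end of treatment.** Section 11.3.13.3 does not say. For subjects who withdraw before Week 16, one footnote to the schedule makes the early termination assessments identical to Week 32, which includes an ECG. The next footnote and the table mark leave the ECG to the investigator. Subjects who only stop product are asked to attend an early termination visit and to keep coming, with Week 16 prioritized (7.4), so they could have two candidate ECGs. In the phase 2a trial, 7 + 11 = 18 of 58 subjects (31%) stopped product and/or withdrew (2.2.2), so the rule could affect a sizeable group.

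**The case against.** The strongest reply is that the findings that matter clinically are already covered. A clinically significant abnormality at any visit is listed, and a new or worsened one becomes an adverse event. It then reaches by-arm tables with subject counts and percentages. That stands, apart from the Week 32 cut-off. A reader might infer that ECGs from Weeks 4, 8 and 32 reach no table of any kind, but the documents do not support that. They reach no ECG table.

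Second, the stated worry in Section 9.2 is about long-term exposure, which favours a late time point. Section 9.1 ties the Week 4 peak to regimen 1 only and predicts steady state by Week 14 for another regimen. A persistent, dose-related effect would show in a by-arm shift at Week 16. So it would be too strong to say that the table cannot show an exposure-related effect. What it cannot show is a transient one, or one first seen in follow-up.

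Third, a reader might infer that early stoppers drop out of the table. The documents do not say so: the Week 16 visit is prioritized for them, and the end-of-treatment form is completed at Week 16 or at early termination, so an early termination ECG may count. The fault is an unstated rule, not a stated exclusion.

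Fourth, Section 11.3.1 provides for a SAP to be finalized before unblinding, and it could add these tables. The text reviewed does not contain them. The general rule that "An observed-cases approach will be used for tabulations of data by visit" says how by-visit tables are built but does not commit to one for ECGs.

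**Conclusion.** The point holds in a limited form. One of four scheduled post-baseline ECG visits feeds an ECG table. Abnormal results without clinical significance, and the by-arm distribution, at Weeks 4, 8 and 32 appear in no planned output, and a shift that resolves by Week 16 is displayed as no change. The count of 750 out of 1,000 ECGs assumes full attendance and that Week 16 supplies the end-of-treatment value.

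No percentage of missed shifts can be given. The documents contain no rate of ECG abnormality and nothing on persistence, and the share captured could run from none (an effect confined to Weeks 4 to 8) to all (a persistent one). No efficacy conclusion and no error rate is affected. This is a desirable improvement to safety reporting rather than an error in the plan.

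**What to change.** In the SAP, before unblinding:

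- Add a by-arm shift table from baseline to the worst post-baseline ECG category, including unscheduled and early termination ECGs, and state whether Week 32 is included.
- Add by-arm shifts at each scheduled visit (Weeks 4, 8, 16 and 32), in line with the by-visit summaries of vital signs and laboratory data.
- State which ECG counts as end of treatment for subjects who stop product early, and reconcile the schedule footnotes on whether the early termination ECG is required.

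The cost is one or two programmed tables from data already collected, with no new procedure for subjects. A worst-category shift will show somewhat more abnormalities in every arm, so it should be read against placebo.

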#### **11.3.13.4 Clinical laboratory evaluation**

The change in each of the laboratory parameters (except from hematology ratios) from baseline to each relevant visit will be summarized as mean, SD, median, minimum, and maximum values for each treatment group.

For liver and kidney parameters (ALP, ALT, AST, BIL, and eGFR) and white blood cells (neutrophils, lymphocytes, and eosinophils), guideline or literature defined thresholds will be used for producing shift tables and categorical threshold tables. The remaining laboratory parameters will be classified as 'low', 'normal', or 'high', depending on whether the value is below, within, or above the reference range and these categories will be used for producing shift tables.

THIS DOCUMENT CONTAINS CONFIDENTIAL INFORMATION AND MUST NOT BE COPIED OR MADE AVAILABLE TO ANY THIRD PARTY  
WITHOUT THE PRIOR WRITTEN CONSENT OF THE LEO PHARMA GROUP

If any subjects have concurrent elevations of alkaline phosphatase, ALT, AST, and bilirubin, per the guideline or literature defined thresholds, an individual profile plot of the subjects' alkaline phosphatase, ALT, AST, and bilirubin over the trial period will be provided.

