### Panel 12: Clinical laboratory tests

Clinical chemistry	Hematology
Sodium Potassium Creatinine Urea nitrogen Calcium Alkaline phosphatase AST ALT Gamma glutamyl transferase Lipase Bilirubin  (Direct bilirubin)  (Indirect bilirubin)  Cholesterol LDL cholesterol and HDL cholesterol Triglycerides Tryptase 	Hemoglobin Leukocytes Neutrophils Neutrophils/leukocytes  Lymphocytes Lymphocytes/leukocytes  Monocytes Monocytes/leukocytes  Eosinophils Eosinophils/leukocytes  Basophils Basophils/leukocytes  Thrombocytes
Serology	Tuberculosis test 
Hepatitis B virus surface antigen  Hepatitis B virus surface Ab  Hepatitis B virus core Ab  Hepatitis C virus Ab  HIV-1 Ab  and HIV-2 Ab  IgE	A tuberculosis test will be performed according to local standard of care for patients requiring initiation of biologic treatment. A tuberculosis test can be performed at the central or local laboratory.
	Serum pregnancy test 
	Choriogonadotropin Beta

THIS DOCUMENT CONTAINS CONFIDENTIAL INFORMATION AND MUST NOT BE COPIED OR MADE AVAILABLE TO ANY THIRD PARTY WITHOUT THE PRIOR WRITTEN CONSENT OF THE LEO PHARMA GROUP

Urinalysis 	Urine pregnancy test 
Protein	Choriogonadotropin Beta
Glucose	
Ketones	
Occult blood	
Leukocytes	
Nitrite	

- 1) If bilirubin is above upper limit of normal, direct and indirect bilirubin will also be measured.
- 2) In case of an anaphylactic reaction, analysis of serum tryptase must be performed (please refer to Section 6.2).
- 3) Conducted at screening. In case additional analyses are needed to support the interpretation of the initial test results for hepatitis B, hepatitis C, or HIV, these will be conducted by the central laboratory, as applicable (e.g. HBV-DNA, HCV-RNA).
- 4) The symbol '/' included in the table represents 'a ratio'.
- 5) Only women of childbearing potential.
- 6) The analytes listed will only be measured if the urine dipstick is abnormal.

**Abbreviations:** Ab = antibody; ALT = alanine aminotransferase; AST = aspartate aminotransferase; HDL = high density lipoprotein; HIV = human immunodeficiency virus; IgE = immunoglobulin E; LDL = low density lipoprotein.

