### Reporting in eCRF

It will be recorded in the eCRF if a blood sample was taken. If not, a reason should be provided. The investigator's assessment of the results ('normal', 'abnormal, not clinically significant', 'abnormal, clinically significant') will also be recorded.

Site staff will record in the eCRF if a urine dipstick was performed and whether urinalysis is required for further assessment, as judged by the investigator. If so, a urine sample should be sent to the central laboratory. If the urine sample was not tested with a dipstick, a reason will be provided. In case urinalysis is performed, the investigator's assessment of the results ('normal', 'abnormal, not clinically significant', 'abnormal, clinically significant') will be recorded in the eCRF.

It will be recorded in the eCRF if the subject is a woman of childbearing potential and if a urine pregnancy test was conducted. If not, a reason should be provided. The date and outcome ('positive', 'negative') of the urine pregnancy test will also be recorded.

Clinically significant abnormal laboratory results at screening (or originating from laboratory tests taken at the screening visit) will be documented as medical history in the eCRF. Any clinically significant worsening of a pre-existing condition or any new clinically significant abnormality occurring after screening will be reported as an AE as described in Section 12.2.4.

Refer to Appendix 1 (Section 12.1.8) for principles for data entry in the eCRF.

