## **10.7 Reporting of other events**

### **10.7.1 AEs of special interest**

Eczema herpeticum is considered an AESI. If available (e.g. as part of the standard clinical practice), the below additional skin findings are to be recorded in the eCRF:

- Lesion type (papules, vesicles, crusts, eroded pits, other).
- Disseminated/localized.
- Location (face, scalp, back, chest, upper limb, lower limb, genitals).
- Present in an area with visible eczema / no visible eczema / present in areas with and without eczema.
- Monomorphic/polymorphic.
- Confirmation of herpes simplex virus (not confirmed, PCR, viral culture, Tzanck, other).

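### The individual liver profile plot is triggered only when alkaline phosphatase, ALT, AST and bilirubin are all raised together, so raised transaminases and bilirubin with normal alkaline phosphatase produce no plot

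*Combined protocol and SAP*

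**What the plan says.** Section 11.3.13.4 (Clinical laboratory evaluation) describes three kinds of output for the liver markers.

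- **Summaries by visit.** Changes from baseline are summarised for each laboratory parameter and treatment group.
- **Tables against thresholds.** For a list of liver and kidney parameters and white cell counts, "guideline or literature defined thresholds will be used for producing shift tables and categorical threshold tables".
- **Individual plots.** The condition is "If any subjects have concurrent elevations of alkaline phosphatase, ALT, AST, and bilirubin, per the guideline or literature defined thresholds", and when it is met "an individual profile plot of the subjects' alkaline phosphatase, ALT, AST, and bilirubin over the trial period will be provided".

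The section gives no numerical thresholds, names no guideline, and does not say what interval counts as concurrent. The analytes come from the central laboratory panel. Panel 12 lists "Alkaline phosphatase AST ALT Gamma glutamyl transferase Lipase", with bilirubin after them.

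Three other provisions bear on the point. Section 8.4.5.2 requires that "Any clinically significant worsening of a pre-existing condition or any new clinically significant abnormality occurring after screening will be reported as an AE". Section 10.7.1 names one event of special interest: "Eczema herpeticum is considered an AESI". Section 11.3.1 says that "the SAP will be finalized before breaking the randomization code". In the text available there is no separate SAP wording that alters the plot condition.

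**The concern.** The plot is the only planned output stated to depend on concurrent elevations within one subject. Tables by parameter show how many subjects crossed each threshold. They need not show whether the same subject crossed two of them at the same time. Whether transaminases and bilirubin rose together in a subject is a question about joint behaviour over time, and the plot is the display meant to answer it.

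Because the condition also demands raised alkaline phosphatase and both transaminases, it excludes subjects in whom the joint time course would still be informative. The report could correctly state that no subject met the concurrent criterion while a subject had ALT, AST and bilirubin all raised together.

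This is a dose-finding trial with 250 subjects in five equal groups, so about 4 × 50 = 200 on active drug. The synopsis records no data monitoring committee or other committee. In a trial of this size a single case would be read individually, so the choice of which subjects are displayed matters more than it would in a large programme.

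**Working it through.** The plan states no figure on this point, so there is none to reproduce. The check is a reading of the condition, a count of patterns, and a search for another output that fills the gap.

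**Step 1: the condition.** Let P, L, S and B stand for alkaline phosphatase, ALT, AST and bilirubin above their thresholds. As written, a plot requires P and L and S and B, concurrently.

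**Step 2: all patterns.** Four markers, each raised or not, give 2^4 = 16 patterns. One of them meets the condition.

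**Step 3: patterns with bilirubin and a transaminase raised.** There are three transaminase states (ALT only, AST only, both) and two alkaline phosphatase states: 3 × 2 = 6.

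| Transaminases (bilirubin raised) | Alkaline phosphatase raised | Alkaline phosphatase normal |
|---|---|---|
| ALT only | no plot | no plot |
| AST only | no plot | no plot |
| ALT and AST | plot | no plot |

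The rule covers 1 of the 6. All 3 with normal alkaline phosphatase are missed, as are 2 with raised alkaline phosphatase but only one transaminase raised.

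**Step 4: the alternative trigger.** The condition (L or S) and B covers all 6. It includes the one pattern plotted now, so no subject currently displayed would be lost.

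**Step 5: other outputs.**

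- *Shift and threshold tables* (11.3.13.4): these include the subject. No combined liver category is specified. The text does not say that the tables are strictly single-parameter, so that remains an inference.
- *Adverse events* (8.4.5.2 and 11.3.13.1): an abnormality judged clinically significant is reported, listed and tabulated. This depends on the investigator's judgement and does not display the joint time course.
- *Narratives* (12.2.6): planned for serious adverse events, deaths and events of special interest. No liver event is of special interest, and 11.3.13.1 gives no narratives for adverse events leading to discontinuation as such. A non-serious combined elevation therefore has no planned narrative.
- *Other triggers*: no other section sets a different condition for an individual liver profile.

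**The case against.** The strongest reply is that only a plot is at stake. The sentence is not a rule for detecting, reporting or stopping. Section 8.4.5.2 has the investigator evaluate and sign every central laboratory result outside the reference range. Under Panel 12, bilirubin above the upper limit leads to direct and indirect bilirubin being measured, whatever the alkaline phosphatase. Clinically significant findings become adverse events and appear in listings, and a medically important one would be a serious adverse event with a narrative. All of this stands, and it limits the point to a gap in display.

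A second reply is that the list may only name the markers to be examined, with the combination left to a guideline and settled in the SAP. The sentence does not say so. The phrase "per the guideline or literature defined thresholds" attaches to thresholds, not to combinations. If another combination was intended, the sentence still needs correcting, because two programmers could produce different sets of plots from it.

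A third reply is that the documents nowhere rank liver patterns, report no serious adverse events in the three completed trials, and name no liver concern. That is fair. The point does not need a ranking or an expected rate. It needs only that concurrent elevation was thought worth displaying and that the condition leaves out most forms of it.

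A reader might go further and infer that the rule favours cholestatic patterns. It does not: raised alkaline phosphatase and bilirubin with normal transaminases also fails it. A reader might also infer that a case could surface only as separate counts in single-parameter tables. The adverse event, listing and narrative routes above contradict that, and the tables are not stated to be single-parameter.

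**Conclusion.** The point holds as a defect in a reporting rule. On its plain reading, Section 11.3.13.4 gives no profile plot to a subject with ALT and/or AST and bilirubin raised and normal alkaline phosphatase, and nothing else in the documents specifies an equivalent joint display.

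Its size is modest. The literal condition is met by 1 of 16 patterns, and by 1 of the 6 that combine bilirubin with a transaminase. These are counts of patterns with no weighting for how often each occurs, so they should not be read as a probability of missing a case. The documents give no expected number of cases. Omitting the display for one subject could affect how liver safety is read; the documents do not support saying that it would.

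The conclusion assumes that the conjunction is meant literally and that no unseen SAP text replaces it. Endpoints, the testing hierarchy, power and clinical management are unaffected. The change is worth making because it is cheap and specific.

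**What to change.** In Section 11.3.13.4 or the SAP, before the randomization code is broken:

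1. Change the plot trigger to ALT or AST above its threshold, concurrent with bilirubin above its threshold, regardless of alkaline phosphatase.
2. Plot ALT, AST, alkaline phosphatase and bilirubin over the trial for each such subject.
3. Report the number of such subjects by arm.
4. State the thresholds and the interval that counts as concurrent, so that the output can be programmed in only one way.

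All four analytes are already in the central laboratory panel, so no additional sampling is needed. The cost is one or two sentences, possibly a few extra plots, and one small table. The change governs reporting only and alters no dosing, discontinuation or monitoring rule.
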